6.1.3. Missing Data Imputation

6.1.3.1. Non-Responder Imputation (NRI)

All subjects who discontinue the study or permanently discontinue the study treatment at any time for any reason will be defined as nonresponders for the NRI analysis for categorical variables, such as ACR20/ ACR50/ ACR70, from the time of discontinuation and onward. If, at the time of study database lock, there are subjects with unresolved interruptions of study drug (ie, not yet re-started, to be confirmed as a temporary interruption, and not yet permanently discontinued), these subjects will be treated as having been permanently discontinued from study drug for the purposes of data imputation for analysis purposes.

6.1.3.2. Modified Last-Observation-Carried-Forward (mLOCF)

For all continuous measures including safety analyses, the mLOCF will be a general approach to impute missing data unless otherwise specified.

For subjects discontinuing from the study or permanently discontinuing the study treatment for any reason, the last nonmissing postbaseline observation before discontinuation will be carried forward to subsequent time points for evaluation. If, at the time of study database lock, there are subjects with unresolved interruptions of study drug (ie, not yet re-started, to be confirmed as a temporary interruption, and not yet permanently discontinued), these subjects will be treated as having been permanently discontinued from study drug for the purposes of data imputation for analysis purposes.

If a subject has a missing observed record (or one imputed by other means) for a postbaseline visit, the last postbaseline record prior to the missed visit will be used for this postbaseline visit.

After mLOCF imputation, data from subjects with nonmissing baseline and postbaseline observations will be included in these analyses.

6.2. Treatment Group Comparability

6.2.1. Subject Disposition

A detailed description of subject disposition will be provided. A summary of the number and percentages of subjects entered, screen failed prior to randomization, randomized in the study, treated, discontinued, and completed the study will be provided. The reason for their discontinuation from the Dosing Period will be provided.

A listing of subject disposition will be provided for all screened subjects, with the extent of their participation in the study and the reason for discontinuation.

6.2.2. Important Protocol Deviations

Important protocol deviations that potentially compromise the data integrity and subjects' safety will be summarized (by treatment group for all mITT subjects).

[Table JPDA.6.1](#) lists the categories, subcategories, and study specific terms of important protocol deviations, source of identification, and the method to identify each deviation.

Table JPDA.6.1. Description of Important Protocol Deviations

Category / Subcategory / Study specific	Source	Methods of Identification	Excluded from the Per Protocol Analysis
Category: Informed Consent			
Informed Consent Not Obtained/Missing/Late	Programmable (Clinical database)	If subject informed consent date is missing or after Visit 1 date	Yes
Category: Eligibility			
Subcategory: Inclusion/Exclusion			
Failed to meet the following eligibility criteria but was still enrolled into the study			
[1] Age ≥ 18 or ≤ 65 yrs	Programmable (Clinical database)	If year of ICD - Year of birth is < 18 years or > 65 years	Yes
[2] positive pregnancy test	Programmable (Clinical database)	If (positive serum pregnancy test at screening or urine pregnancy test at baseline) and subject has visit, Positive pregnancy test by central lab at screening or local lab UPT at baseline	Yes
[5] diagnosis of RA for at least 6 months prior to screening	Programmable (Clinical database)	If Visit 1 - RA diagnosis date is less than 180 days (6 months)	Yes
[6] either positive test results for RF or ACPA at screening OR Previous radiographs documenting bony erosions	Mixed [non-programmable (Monitoring) and Programmable (Clinical database)]	Should have documentation of previous radiographs of bony erosions in hands or feet. If RF and ACPA are negative and no documentation of previous radiographs of bony erosions in hands or feet.	Yes
[7] active RA	Programmable (Clinical database)	Part A: at least 3 swollen joints Part B: at least 6 swollen joints, 6 tender joints, hs-CRP $>$ ULN or positive test result for ACPA	Yes
[8] prior DMARD treatment (Part B)	Programmable (Clinical database)	At least 1 prior therapy is reported for Rheumatoid Arthritis	Yes
[11] prior enrollment in study	Non-programmable (Monitoring)	Any documentation indicate same subjects enroll to Part A and B.	Yes
[12] received synthetic immunosuppressive therapies under the defined conditions	Programmable (Clinical database)	Changing dosing of methotrexate, hydroxychloroquine, sulfasalazine, or leflunomide before Visit 2. If Visit 1 – stop date of MTX plus leflunomide, gold salts, kinase inhibitors (such as tofacitinib), cyclophosphamide, mycophenolic acid, azathioprine, cyclosporine, sirolimus, or tacrolimus +1 is less than 28 days.	Yes

Category / Subcategory / Study_specific	Source	Methods of Identification	Excluded from the Per Protocol Analysis
[13] received biologic immunosuppressive therapies under the defined conditions	Programmable (Clinical database)	
If Visit 2 (Visit 102 for Part B)- stop date of etanercept, adalimumab, or anakinra +1 is less than 14 days.
 
If Visit 2 (Visit 102 for Part B)- stop date of infliximab, certolizumab pegol, golimumab, abatacept, or tocilizumab +1 is less than 28 days (4 weeks).
 
If Visit 2 (Visit 102 for Part B) – stop date of belimumab, natalizumab, or vedolizumab + 1 is less than 180 days (6 months).
 
PART A: if Visit 1(Visit 101 for Part B) – stop date of B-cell-depleting agents (such as rituximab) or other cell-depleting biologics (eg, anti-CD3 antibody) + 1 is less than 365 days (12 months).
 
PART B: if subjects used B-cell-depleting agents (such as rituximab) or other cell-depleting biologics (eg, anti-CD3 antibody)
	Yes
[14] and [32] received other types of therapies, including investigational, under the defined conditions	Non-Programmable (monitoring)	
Any documentation of parenteral corticosteroids used or planned to be used, oral prednisone (or equivalent), chronic narcotic drug, gemfibrozil (a strong cytochrome P450 2C8 inhibitor) or alfentanil, dihydroergotamine, dofetilide, ergotamine, fentanyl, pimozide, or quinidine (sensitive narrow therapeutic index cytochrome P450 3A substrates)
 
Any documentation of involving an investigational product (IP) or any other type of medical research or have received any of the following IPs under the defined conditions: any nonbiologic IP within 5 half-lives prior to baseline, any leukocyte-depleting agent (eg, anti-CD22 or anti-CD3) at any time, any non-cell depleting biologic IP within 90 days or 5 drug half-lives (whichever is longer) prior to screening. If unknown half-lives, consider this case as more than 5 drug half-lives.
	Yes
[15] and [16] clinically significant safety labs at screening	Programmable (Clinical database)	if any of lab result for selected lab tests is outside of exclusionary range (stated in protocol exclusion 15 & 16) at screening	No
[17], [18],[19] Evidence of hepatitis B, C or HIV	Programmable (Clinical database)	If HIV, HBV, or HCV is positive at screening.	Yes

Category / Subcategory / Study specific	Source	Methods of Identification	Excluded from the Per Protocol Analysis
Category: Investigational Product			
Treatment Assignment	Non Programming (Monitoring)	Dispensing error: Subject is assigned to A, but site gave B to the subject	Yes
Dosing Error	Non Programmable (Monitoring)	- All issues referred to Incorrect dosing	Yes
Non-Compliance	Programmable (clinical database)	Treatment compliance below 80% or over 120%	Yes
Shipment and Storage	Non Programmable (Monitoring)	Temperature control for drug storage or biological samples not kept	Yes
Drug Accountability	Non Programmable (Monitoring)	- IP was not returned by subject/IP lost by subject or at site - Empty or unused IP packaging was not returned or lost by the subject more than once	No
Unblinding	Non Programmable (Monitoring)	- Any inadvertent unblinding affecting, subjects, investigator or sponsor	Yes, for any visit after the unblinding?
Category: Study Procedures			
Excluded Con-Meds	Mixed (Clinical database and Monitoring)	Study specific Definition: a list with all concomitant medication will be generated, and CRP will flag those excluded (the flagged medications will be used in programming to flag important protocol deviations)	Yes
Category: Administrative/Oversight			
Subcategory:			
Improper Conduct of Assessments	Non Programmable (Monitoring)	Unauthorized/Unqualified site personnel perform study related activities. Study personnel training not performed, not properly documented Non Programmable (Monitoring)	Yes
Suspected Misconduct	Non Programmable (Monitoring)	- Site staff sharing IWRS, EDC or ePresentOnline account details - Suspected falsification of data	Yes if suspected falsification of data
Category: Safety			
Subcategory:			
Safety Mailings	Non Programmable (Monitoring)	Lack, significant delay in safety mailing review (significant delay defined as a delay of 6 months)	No

Category / Subcategory / Study_specific	Source	Methods of Identification	Excluded from the Per Protocol Analysis
SAEs	Non Programmable (Monitoring)	- Failure to report an SAE within 24 hours of the investigator being made aware of the SAE - Failure to respond to SAE queries	No
AEs	Non Programmable (Monitoring)	Failure to record AEs in the data capture system	No

Abbreviations: AE = adverse event; Con-Meds = concomitant medications; CRF = case report form; CRP = clinical research physician; EDC = electronic data capture; ICD = informed consent document; IP = investigational product; IWRS = interactive Web Response System; PK = pharmacokinetics; SAE = serious adverse event.

Subjects with 1 or more such deviations will be excluded from the per protocol (PP) population. In addition, subjects must complete 12 weeks of study drug to be included in the PP population. The listing of important protocol deviations for all mITT subjects during the entire study, with the indication of whether to be excluded from the PP population, will also be provided.

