- parenteral corticosteroids within 28 days prior to baseline or planned treatment during the study. (A single intra-articular corticosteroid injection is permitted within 28 days prior to baseline if no more than 40 mg triamcinolone [or equivalent] is administered and no further injections are planned during the study. The treated joint should be excluded from any joint-specific evaluations during the study.)
- prescription for oral prednisone (or equivalent) >10 mg/day or UNSTABLE PRESCRIBED DOSE within 28 days prior to baseline
- a chronic narcotic drug at an UNSTABLE PRESCRIBED DOSE within 28 days prior to baseline or planned increase/new prescription during the study
- gemfibrozil (a strong cytochrome P450 2C8 inhibitor) or alfentanil, dihydroergotamine, dofetilide, ergotamine, fentanyl, pimozone, or quinidine

(sensitive narrow therapeutic index cytochrome P450 3A substrates) within 28 days prior to baseline or planned treatment during the study

[15] have any clinically significant hematological or chemistry abnormalities at screening, including

- hemoglobin level <8.5 g/dL (<85 g/L)
- total platelet count <100 × 10⁹/L (<100 × 10³/μL or <100 Gi/L)
- total white blood cell count <3.0 × 10⁹/L (<3.0 × 10³/μL or <3.0 Gi/L)
- aspartate aminotransferase (AST) level >2.5 × ULN
- alanine aminotransferase (ALT) level >2.5 × ULN
- creatinine level ≥1.5 mg/dL (≥129 μmol/L)
- amylase >1.5 x ULN
- lipase >1.5 x ULN

A single repeat analysis is allowed according to investigator judgment prior to making a final determination of eligibility. The repeat laboratory test does not require a re-consent because the result does not constitute a screening failure until the clinically significant, out-of-range value is confirmed.

[16] have known hypogammaglobulinemia or a screening serum IgG level <565 mg/dL (<5.65 g/L)

A single repeat analysis is allowed according to investigator judgment prior to making a final determination of eligibility. The repeat laboratory test does not require a re-consent because the result does not constitute a screening failure until the clinically significant out-of-range value is confirmed.

[17] have evidence of or test positive for hepatitis C virus (HCV) at screening (defined as a positive test result for hepatitis C antibody [anti-HCVAb] plus a positive confirmatory test result for HCV [eg, HCV RNA])

Subjects whose results are anti-HCVAb positive and HCV RNA negative can be enrolled in the study, according to investigator judgment.

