[18] have evidence of or test positive for hepatitis B virus (HBV) at screening, defined as (1) testing positive for hepatitis B surface antigen OR (2) testing positive for anti-hepatitis B core antibody (HBcAb) AND positive for HBV DNA

Subjects whose results are HBcAb positive and HBV DNA negative may be enrolled in the study, according to investigator judgment. Subjects whose results are HBcAb positive and HBV DNA negative at screening will be monitored for HBV during the study as detailed in Section 8.4.7.1.

[19] have evidence of or test positive for human immunodeficiency virus at screening

[20] have symptomatic herpes zoster within 6 months prior to screening that constitutes a clinically significant risk to the subject (according to investigator judgment)

- [21] have active tuberculosis (TB) determined on the basis of a positive medical history, physical examination, or chest radiography (per local standard of care) or have exclusionary TB test results, which include either of the following:
- a positive tuberculin skin test (TST) result (defined as a skin induration >5 mm at 48 to 72 hours after the test date, regardless of Bacillus Calmette-Guérin vaccination history) or
 - a positive (or persistently indeterminate/invalid/borderline) interferon γ release test (eg, QuantiFERON[®]-TB Gold or T-Spot[®].TB)

The choice to perform either a TST or an interferon γ release test will be made by the investigator according to local licensing and standard of care. If the QuantiFERON-TB Gold is indeterminate or the T-Spot.TB is invalid or borderline, one retest is allowed according to investigator judgment. If the repeat test is also indeterminate, the subject will be excluded. The interferon γ release test can be used only in countries where it is licensed, and the use of this test is dependent on previous treatment(s).

Subjects with known latent TB should not undergo a TST or interferon γ release test and must have documentation of receiving at least 4 weeks of appropriate, ongoing latent TB therapy, according to local standard of care, prior to screening. Such patients must continue/complete appropriate latent TB therapy during the course of the study in order to remain eligible.

- [22] are at high risk of infection or have recent evidence of clinically significant infection, based on findings that include the following:
- fever of 100.5°F (38°C) or above at screening or baseline that is not due to the underlying autoimmune disease (eg, RA)

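### Some per-protocol identification rules in SAP Table JPDA.6.1 do not match the protocol criteria they check, so the set could drop eligible subjects and keep ineligible ones if the rules are applied as written

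*SAP*

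**What the plan says.** SAP 6.2.2 defines important protocol deviations in Table JPDA.6.1. Each row gives a source (programmed from the database, or monitoring), a method of identification, and whether the deviation removes the subject from the per-protocol analysis. The rows at issue are marked Yes for removal; the unblinding cell is a qualified Yes.

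- **Row [12], programmable:** flags "Changing dosing of methotrexate, hydroxychloroquine, sulfasalazine, or leflunomide before Visit 2". It counts methotrexate plus leflunomide, together with several other agents, from Visit 1 with a +1.
- **Row [1], programmable:** "If year of ICD - Year of birth is < 18 years or > 65 years".
- **Row [13], programmable:** flags if baseline minus "stop date of etanercept, adalimumab, or anakinra +1 is less than 14 days", with the same form for the longer washouts.
- **Row [14], monitoring:** "Any documentation of parenteral corticosteroids used or planned to be used, oral prednisone (or equivalent), chronic narcotic drug", followed by a list of interacting drugs.
- **Unblinding, monitoring:** "Yes, for any visit after the unblinding", followed by a question mark.

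On oral steroids, Protocol 5.2 criterion [14] excludes only a "prescription for oral prednisone (or equivalent) >10 mg/day or UNSTABLE PRESCRIBED DOSE within 28 days prior to baseline". SAP 6.3.2 names the per-protocol analysis of ACR20 as a sensitivity analysis, and SAP 6.1.1 extends the per-protocol set to key secondary efficacy analyses.

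**The concern.** Protocol Appendix 1 describes the per-protocol set as the subjects who complied sufficiently with the protocol. A subject who met every criterion should therefore not leave it on eligibility grounds, and one who failed a criterion should not stay in unnoticed. For programmable rows the method text is in effect the specification for the code, so a wrong rule becomes a wrong flag. For monitored rows, wording that allows two readings allows two different per-protocol sets.

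What is at stake is how the per-protocol result can be read. If it differed from the primary result, nobody could say whether protocol violations or mis-specified flags were the cause. If the set shrank a good deal, a null per-protocol result would say little.

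**Working it through.** **1. The plan's own figure.** Inputs from SAP 5.2 and Protocol 9.1: placebo 30%, active 30% + 25% = 55%, two-sided alpha 0.05, 61 per arm. With pooled variance under the null and mean rate 0.425:

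power = Φ{[0.25√n − 1.96·√(2·0.425·0.575)] / √(0.30·0.70 + 0.55·0.45)} = Φ{(0.25√n − 1.370)/0.676}

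At n = 61 this is Φ(0.861) = 80.5%, and 61 is the smallest n that reaches 80%. The stated sample size reproduces.

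**2. Row against criterion.**

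| Row | SAP rule | Protocol criterion | Effect if applied as written |
|---|---|---|---|
| [12], dose change | Any change before Visit 2; no Part B visit number | Prescription change within 28 days before baseline, or a planned change during the study | Flags an eligible subject whose change was longer ago |
| [12], methotrexate plus leflunomide | Counted from Visit 1 | Within 28 days before baseline | Flags eligible subjects (below) |
| [1] | Year of consent minus year of birth | Age 18 to 65 inclusive at initial screening | Errs in both directions (below) |
| [13], and the washout in [12] | Visit date − stop date + 1 below the limit | Limit in days before the visit | Washout one day short |
| [14] | Any documented oral prednisone or chronic narcotic | Prednisone above 10 mg/day or unstable within 28 days before baseline; narcotic unstable in that window or with a planned increase or new prescription; one limited intra-articular injection permitted | Read literally, flags permitted users |

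- **[12], combination.** Screening may last 28 days. After a full 28-day screening, a subject who stopped the combination the day before Visit 1 stopped 29 days before baseline, outside the protocol window. The SAP count is 1 + 1 = 2, below 28, so the subject is flagged.
- **[1].** With consent in year Y, a subject born in Y − 66 whose birthday is still to come is 65 and eligible, but the difference is 66 and the flag fires. A subject born in Y − 18 whose birthday is still to come is 17, but the difference is 18 and no flag fires.
- **[13].** A stop 13 days before baseline gives 13 + 1 = 14, which is not below 14, so it escapes the 14-day rule.

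**3. Size of a literal row [14].** The documents give no share of subjects on oral steroid, so the share s is assumed, equal across arms, with response rates unchanged in those who remain. Then n = 61(1 − s), put into the formula above. The 95% half-width for the risk difference is 1.96·√(0.4575/n), which is 17.0 points at n = 61.

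| s (assumed) | Dropped of 244 | n per arm | Power | Half-width (points) |
|---|---|---|---|---|
| 10% | 24 | 54.9 | 76.2% | 17.9 |
| 20% | 49 | 48.8 | 71.1% | 19.0 |
| 30% | 73 | 42.7 | 65.2% | 20.3 |
| 40% | 98 | 36.6 | 58.3% | 21.9 |
| 50% | 122 | 30.5 | 50.6% | 24.0 |
| 60% | 146 | 24.4 | 42.1% | 26.8 |

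Losses from discontinuation and other deviations come on top. No comparable range can be given for row [12], because the documents do not say how much dosing history is recorded.

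**The case against.** The strongest defence concerns row [14]. It stands under a sub-heading about subjects enrolled despite failing a criterion, its label refers back to the protocol's conditions, and monitors apply it, not a program. A monitor could reasonably flag only true failures of criterion [14]. That stands, and it means the row is ambiguous, not plainly wrong. It does not clear the row: the investigational-product half of the same cell repeats the protocol's time limits while the steroid and narcotic half omits them. Nor does it help rows [1], [12] and [13], which are programmable. The missing Part B visit number in row [12] is minor, since the Part B schedule itself uses V2 loosely for baseline; the missing 28-day window is not.

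A reader might infer more than the documents support:

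- **That permitted hepatitis subjects are dropped.** The SAP flags "If HIV, HBV, or HCV is positive at screening", while the protocol says "Subjects whose results are HBcAb positive and HBV DNA negative may be enrolled in the study", at the investigator's judgment. But criteria [17] and [18] define testing positive to include the confirmatory RNA or DNA result, except that surface antigen alone suffices for hepatitis B. Read with that definition, the rows agree.
- **That rows marked No also exclude.** The closing sentence of SAP 6.2.2 is loose, but the Yes/No column, the promised listing and the reference in SAP 6.1.1 to specified violations limit exclusion to Yes rows.
- **That completers seen early in the Week 12 window are lost.** This needs 12 weeks of drug to mean 84 days, which neither document says.

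The documents also claim no power for the per-protocol analysis, so the power figures measure lost information and not a broken promise. Protocol 6.3 already requires an unblinded subject to be discontinued unless an exception is approved, so few cases should turn on the unblinding cell.

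**Conclusion.** The mismatch holds for rows [1], [12] and [13] as written, and row [14] is ambiguous. The errors run both ways: [12] and a literal [14] remove eligible subjects, the +1 keeps some who should be flagged, and [1] does both. The unblinding rule is unfinished. Membership of the per-protocol set therefore cannot be reproduced reliably from the SAP.

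The size is conditional. Under a literal row [14] and an assumed 10% to 60% on oral steroid, about 24 to 146 of 244 subjects are lost and power falls from 80.5% to between 76% and 42%. It may be tempting to conclude that the analysis would become a largely steroid-free subset, or that prednisone is the main source of loss. The documents do not support either. SAP 6.5.1 plans a concomitant-steroid subgroup, so users are expected, but no rate is given, and row [12] might flag as many.

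The primary mITT analysis with non-responder imputation (SAP 6.3.1) does not use this table. This is a defect in a supporting analysis, worth correcting because the correction is cheap.

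**What to change.** Before unblinding, reconcile each row with its protocol criterion by citing that criterion in full as controlling.

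- **[14]:** carry the dose, stability and time conditions, the parenteral and intra-articular conditions, and the narcotic planned-increase and new-prescription limbs.
- **[12]:** state the 28-day window before baseline and planned changes during the study, use Visit 102 for Part B, and count methotrexate plus leflunomide from baseline.
- **[12] and [13]:** drop the +1 from the day counts.
- **[1]:** use calculated age at screening, as exact as the collected birth date allows; SAP 6.2.3 already plans to calculate age.
- **Unblinding:** replace the question with a rule, for example excluding subjects unblinded before the Week 12 assessment.

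As clarifications only: name the confirmatory hepatitis tests, state that only Yes rows exclude, and define 12 weeks of drug as dosing to an in-window Visit 106.

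The cost is an edit to one SAP table, reprogramming of a few flags, and an instruction to monitors. No new data collection is needed.
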